#### 5.1.2. IntellaNav StablePoint RC03 Catheter Cable

The IntellaNav™ StablePoint Catheter Cable connects the IntellaNav™ StablePoint Ablation Catheter to the RHYTHMIA HDx™ Mapping System Connection Box. The cable transmits RF energy to the IntellaNav StablePoint catheter and facilitates transmission of signals from the electrodes, force sensor, temperature sensors, location sensor, and catheter identifier. The catheter cable is a 6.6-ft- (200 cm) long flexible electrical cable with identical 41-pin locking connectors on each end. The cable is supplied sterile and should be treated as a single use device for this study.

#### 5.1.3. IntellaNay StablePoint Connection Box

The IntellaNav StablePoint Connection Box (StablePoint Connection Box) is an accessory used with the RHYTHMIA HDx™ Mapping System to connect the IntellaNav StablePoint Catheter (via the IntellaNav StablePoint Catheter Cable) to both the Signal Station and the RF Generator. The StablePoint Connection Box is a reusable, non-sterile, and non-patient contacting.

The StablePoint Connection Box routes intracardiac signals and location and force information sensed by the ablation catheter to the mapping system and prevents RF energy from affecting catheter localization and other mapping system features. The StablePoint Connection Box also passes catheter tip temperature and catheter tip impedance information, as well as RF energy between the RF generator and ablation catheter. Additionally, the StablePoint Connection Box contains the hardware required for measuring the force from the sensors in the Catheter. When using this device, investigators should follow the standard operating procedure of the electrophysiology lab or the directions for use contained in the manufacturer's operator's manual for equipment set-up and operation.

### 5.1.4. Force Computation Software (SW) Module

The Force Computation SW Module interfaces with the IntellaNav StablePoint Force Sensing catheter and calculates the force magnitude and direction. It is installed on the RHYTHMIA HDx™ Mapping System Signal Station. When the Force Computation SW Module is installed, and a compatible IntellaNav StablePoint Catheter is connected to the RHYTHMIA HDx™ Mapping System, the force visualization features become available to the user. While force computation is performed by the Force Computation SW Module, force visualization is performed by the RHYTHMIA HDx™ software version 4.0.1 or greater.

# 5.2. Additional Commercial Systems

The IntellaNav StablePoint Catheter System must be used with additional ancillary products to complete an EP ablation procedure.

## 5.2.1. RHYTHMIA HDxTM

The IntellaNav StablePoint ablation catheter is designed to be used with the BSC RHYTHMIA HDx™ Mapping System (and associated accessories) for mapping and navigation, and visualization of contact force and DIRECTSENSE™ throughout an electrophysiology procedure. The RHYTHMIA HDx™ Mapping System is a catheter-based atrial and ventricular mapping system designed to acquire data from multiple electrodes in order to display 3D anatomical and electroanatomical maps of the human heart in real-time. Additionally, the RHYTHMIA HDx™ Mapping System enables the ability to track compatible catheter locations within the heart, visualize the position relative to the constructed anatomical shell, and acquires and displays intracardiac electrogram signals. The RHYTHMIA HDx™ is required for enabling the capability of the DIRECTSENSE™ feature. This feature allows for an impedance-based metric that can be used in conjunction with other clinical diagnostic measures (e.g., electrogram amplitude, fluoroscopy, intracardiac echocardiography, magnetic and impedance navigation, and tactile feedback) to inform catheter stability and navigation within the heart.

Use of the RHYTHMIA HDx™ Mapping System is required for the study procedure. Prior to the start of the case, site staff must ensure that the RF Generator, IntellaMap Orion mapping catheter, patch kits, and other required or allowed equipment is properly connected to the RHYTHMIA HDx™ Mapping System per the RHYTHMIA HDx™ Hardware IFU.

### 5.2.2. Rhythmia Software 4.0.1 or greater

This study requires the use of Rhythmia software 4.0.1 or greater on the RHYTHMIA HDx™ Workstation. The software processes data received from the signal station and provides a user interface for system operation. It also performs ECG and intracardiac signal display, catheter localization and tracking, 3D mapping and visualization, and diagnostic stimulation routing. Rhythmia software 4.0.1 or greater with the Force Computation Software Module is used to provide force and DIRECTSENSE™ visualization for the IntellaNav StablePoint Catheter System. Additional features are enabled by Rhythmia Software 4.0.1 or greater, such as AutoTag, to enable efficient workflows based on the user's preference.

# 5.2.3. Generator/Pump

The catheter, cable and connection box are designed to transmit RF energy from an RF generator to the tip electrode and return feedback metrics like impedance and tip temperature

back to the RF generator. The Force Sensing System is only compatible with the BSC OI Cardiac Ablation System, which consists of the Maestro 4000 RF Generator, MetriQ™ Irrigation Pump and MetriQ™ Irrigation Tubing Set.

## 5.2.4. Maestro 4000 Radiofrequency Controller

The Maestro 4000 Cardiac Controller is a non-sterile RF Generator specifically designed for cardiac ablation. It produces user-selectable power-controlled or temperature-controlled RF power output in the range of 0 to 150 watts into a nominal tissue impedance of 100 ohms. It delivers RF power via a monopolar method driving current between a single active electrode at the tip of the ablation catheter and one or two dispersive pads applied on the skin. The Maestro 4000 generator interfaces with the investigational catheter via the Maestro 4000 pod (150W or 100W available depending on geography) and the IntellaNav StablePoint Connection Box. Once connected, the Maestro 4000 automatically recognizes the IntellaNav StablePoint catheter (via the resistor ID) as a member of the BSC OI platform. This limits the power to a maximum of 50W and establishes power-controlled mode. When connected to the irrigation pump, the RF Generator communicates with the MetriQ™ Irrigation Pump to coordinate delivery of RF energy with irrigation flow to the catheter tip. Generator settings per RF application can be communicated to a recording system and/or a mapping system via a serial cable connection.

## 5.2.5. MetriQTM Irrigation Pump

The MetriQ™ Pump is a non-sterile peristaltic pump used during RF Cardiac Ablation interventional procedures with open irrigation ablation catheters. The pump provides a single channel of continuous flow through the Tubing Set and the irrigation lumen of the IntellaNav StablePoint. The flow rate is controlled such that the fluid exits the ports in the tip electrode in a predictable manner. Three flow rates can be programmed; a standby flow rate, a low power flow rate and a high-power flow rate. When used with the Maestro 4000 in automatic mode, the generator tells the pump which of the three programmed flow rates to use based on the RF power settings for each RF application.

## 5.2.6. MetriQTM Irrigation Tubing Set

The MetriQ™ Tubing Set is a sterile, disposable tubing assembly which consists of a drip chamber with intravenous (I.V.) spike for connection to the irrigation source, a peristaltic section that is loaded around the pump head, and a standard luer fitting for connection to Boston Scientific Open-Irrigated Ablation Catheters. The tubing set is designed to operate with the MetriQ™ Irrigation Pump, for use in the administration of irrigation solution into the patient through a Boston Scientific Open-Irrigated Ablation Catheter. A four-way stopcock is included.

Released

W and 100W Maestro 4000 Pods are both approved devices in the EU. The 150W Maestro 4000 Pod is the only approved Maestro Pod accessory in the US.

## 5.2.7. IntellaMap Orion

Use of the IntellaMap Orion is required for the study procedure. This high-resolution mapping catheter will be used to create electroanatomical maps throughout the procedure. Subsequent versions of the IntellaMap Orion mapping catheter may be used during this study as they become commercially available after regulatory approval in their geography.

## 5.3. Intended Use and Contraindications

## 5.3.1. Force Sensing System Intended Use / Indications for Use within the U.S.

The StablePoint Connection Box and Cable are indicated for use with the IntellaNav StablePoint Catheter, RHYTHMIA HDx™ Mapping System, and Maestro 4000 RF Generator during an electrophysiology procedure for cardiac electroanatomical mapping, intracardiac stimulation (pacing), recording of electrical potentials, and ablations, The IntellaNay StablePoint Catheter, when used with a compatible Radiofrequency Controller and Irrigation Pump, is indicated for:

- Cardiac electroanatomical mapping
- Delivering diagnostic pacing stimuli
- RF ablation of sustained or recurrent type 1 atrial flutter in patients age 18 years or older
- Treatment of drug refractory, recurrent symptomatic, Paroxysmal Atrial Fibrillation (PAF) in patients age 18 years or older, when used with a compatible mapping system.

## 5.3.2. Force Sensing System Intended Use / Indications for Use outside the U.S.

The IntellaNav StablePoint Catheter and Force Sensing System received CE mark on June 5, 2020 and will be commercially available in geographies that accept CE mark. In certain geographies that do not accept CE mark, the System will be considered investigational. Please refer to the country specific Intended/Indication for Use for additional information on intended use and indications.

# 5.3.3. Contraindications within the U.S.

There are no contraindications for the StablePoint Connection Box, StablePoint Catheter Cable, and Computation Software Module. The IntellaNav StablePoint Catheter is contraindicated for use:

- in patients with active systemic infection
- in patients who are implanted with a mechanical prosthetic heart valve through which the catheter must pass

- in patients who are unable to receive heparin or an acceptable alternative to achieve adequate anticoagulation
- in patients who have vena cava embolic protection filter devices and/or known femoral thrombus who require catheter insertion from the femoral approach
- in patients who are hemodynamically unstable
- in patients with conditions where insertion into or manipulation in the cardiac chambers is unsafe as this may increase the risk of perforation or systemic embolic event, such as but not limited to, evidence of myxoma, Left Atrial (LA) thrombus, or intracardiac mural thrombus
- in patients with a contraindication to an invasive electrophysiology procedure where insertion or manipulation of a catheter in the cardiac chambers is deemed unsafe, such as but not limited to, a recent previous cardiac surgery; e.g., ventriculotomy or atriotomy, Coronary Artery Bypass Graft (CABG), PTCA/PCI/coronary stent procedure/unstable angina, or in patients with congenital heart disease where the underlying abnormality increases the risk of the ablation, severe rotational anomalies of the heart or great vessels
- via transseptal approach in patients with an intraatrial baffle or a foramen ovale patch
- via the retrograde transaortic approach in patients who have had aortic valve replacement

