#### 5.3.4. Contraindications outside the U.S.

Contraindications outside of the U.S. may be different. Centers participating in geographies outside of the U.S. will follow their country specific contraindications for the IntellaNav StablePoint Catheter System based on whether it is considered investigational or commercial in their region. Please refer to the country specific contraindications for additional information in specific regions.

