#### 7.2.1. Treatment

All enrolled subjects who undergo the ablation procedure must be treated with the IntellaNav StablePoint Catheter System.

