- 22. Any carotid stenting or endarterectomy
- 23. Stage 3B renal disease or higher (estimated glomerular filtration rate, eGFR <45 mL/min)
- Known coagulopathy disorder (e.g. von Willebrand's disease, hemophilia)
- Any known contraindication to an AF ablation
- Any known contraindication for anticoagulation (e.g. patients unable to receive heparin or an acceptable alternative to achieve adequate anticoagulation)

- 27. Vena cava embolic protection filter devices and/or known femoral thrombus that prevents catheter insertion from the femoral approach
- Known sensitivity to contrast media (if needed during the procedure) that cannot be controlled with pre-medication
- Rheumatic Heart Disease
- 30. Presence of intramural thrombus, tumor or other abnormality that precludes vascular access, or manipulation of the catheter
- 31. Subjects unable or unwilling to complete follow-up visits and examinations for the duration of the clinical study
- 32. Subjects who are currently enrolled in another investigational study or registry that would directly interfere with the current study, except when the subject is participating in a mandatory governmental registry, or a purely observational registry with no associated treatments; each instance must be brought to the attention of the sponsor to determine eligibility.

†LVEF and LA diameters obtained ≤180 days prior to enrollment will be acceptable, unless a cardiac event has occurred (e.g. MI) between the date of the exam and the enrollment date. In this case, a new echocardiogram (trans-thoracic or trans-esophageal, or intracardiac echo) must be performed to confirm eligibility prior to performing ablation. If no recent (≤180 days prior to enrollment) echocardiogram is available at the time of the enrollment, a new echocardiogram must be performed either prior enrolling the patient into the study or post-consent to confirm patient's eligibility prior to performing the ablation. For TTE, LA anteroposterior diameter measured by M-mode from the parasternal long-axis view will be used. If both LA diameter and volume are available and at least one of them meets the exclusion criteria, the subject is considered ineligible for the study.

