### 10.6.2.2. Pulmonary Vein Isolation

The ablation procedure will consist of Pulmonary Vein Isolation of all pulmonary veins with the IntellaNav StablePoint Catheter System (i.e. IntellaNav StablePoint Cather, Cable and

Connection Box and the Force Computation Software Module). A point by point workflow is highly recommended, however, physicians will follow their preferred ablation workflow and standard of care while utilizing the IntellaNav StablePoint Catheter following all applicable Instructions for Use. The IntellaNav StablePoint Catheter should be inserted via Femoral access with a single or double transseptal puncture at the Investigator's discretion. Cardioversion is permitted prior to or during the ablation procedure at the Investigator's discretion and will be documented.

The IntellaNav StablePoint Catheter System must be used to complete all PV ablations, but multiple catheter curves may be utilized without a deviation or impact to acute procedural success.

Investigators are encouraged to perform Wide Area Circumferential Ablation maintaining 1-2 cm outside the PV ostium to prevent PV stenosis. Ipsilateral PVs may be isolated together or individually based on physicians' preferred workflow. Technique will be documented.

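### At U.S. sites, a patient with a known femoral thrombus that does not prevent femoral insertion is contraindicated under Section 5.3.3 but not excluded by criterion 27

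*Combined protocol and SAP*

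**What the plan says.** Section 5.3.3, which applies within the U.S., lists patients in whom the catheter is contraindicated. One entry reads: "in patients who have vena cava embolic protection filter devices and/or known femoral thrombus who require catheter insertion from the femoral approach". Section 5.3.4 limits its reach: "Contraindications outside of the U.S. may be different".

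Exclusion 27, worded identically in the synopsis and in Table 8-2 (Section 8.3), reads: "Vena cava embolic protection filter devices and/or known femoral thrombus that prevents catheter insertion from the femoral approach".

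Two other sections decide who meets the Section 5.3.3 condition. Section 10.6.2.2 says "The IntellaNav StablePoint Catheter should be inserted via Femoral access", and Section 7.2.1 says "All enrolled subjects who undergo the ablation procedure must be treated with the IntellaNav StablePoint Catheter System".

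Three further texts might cover the same patients:
- exclusion 25: "Any known contraindication to an AF ablation";
- exclusion 30: "Presence of intramural thrombus, tumor or other abnormality that precludes vascular access, or manipulation of the catheter";
- the conduct rule in Section 10.6.2.2, under which physicians follow their usual workflow "while utilizing the IntellaNav StablePoint Catheter following all applicable Instructions for Use".

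**The concern.** The contraindication and the exclusion criterion name the same two conditions but qualify them differently. Section 5.3.3 asks whether the patient requires the femoral route. Exclusion 27 asks whether insertion by that route is prevented. Where femoral access is the study route, the first test catches almost everyone with the condition, and the second catches only some of them.

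Two things are at stake. The first is patient safety: the eligibility table, read alone, can admit a patient in whom the device section says the catheter should not be used. The second is who is analysed. Section 9.5.1 makes anyone later found not to meet the eligibility criteria Consent Ineligible, including by oversight. Such subjects have no follow-up reporting requirements and are left out of the endpoint analyses. Under Section 9.5.4 an eligible subject who receives RF energy is included in all analyses, and Section 11.3.1 builds the safety set from Attempt and Treatment subjects. Thromboembolism and major vascular access complications are both primary safety events (Section 6.1). If eligibility can be read either way, so can the question of whether such an event counts, and it could be argued after the event is known.

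**Working it through.** No formula applies and the plan gives no figure to reproduce. The check sets the passages side by side.

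**Step 1: who meets the Section 5.3.3 condition?** The entry needs a filter and/or known femoral thrombus, plus a requirement for femoral insertion. Section 10.6.2.2 makes femoral access the study route, and Section 7.2.1 leaves no other ablation system. The second part is therefore met for essentially every ablated subject. I say essentially because Section 10.6.2.2 uses *should* and not *must*.

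**Step 2: apply both rules to each kind of U.S. patient.**

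| Patient | Section 5.3.3 | Exclusion 27 | Agree? |
|---|---|---|---|
| Known femoral thrombus that prevents femoral insertion | Contraindicated if treated by the study route | Excluded | Yes |
| Known femoral thrombus that does not prevent it | Contraindicated | Not excluded | **No** |
| Filter, if *prevents* qualifies thrombus only | Contraindicated | Excluded | Yes |
| Filter that does not prevent insertion, if *prevents* qualifies both nouns | Contraindicated | Not excluded | **No** |

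The second row conflicts on any reading. The last two rows depend on grammar. The singular verb agrees with thrombus and not with devices, which favours the narrow reading, but the sentence does not rule out the other.

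**Step 3: do other texts remove the conflict?**
- Exclusion 25 concerns contraindications to AF ablation. It does not refer to this catheter's list, and exclusion 27 deals with this exact condition by its own test.
- Exclusion 30 applies only where access or manipulation is precluded, so it has the same limit as exclusion 27.
- The instructions-for-use clause governs how the catheter is used. It is not an eligibility criterion.
- No exclusion criterion refers to the Section 5.3.3 list as such.

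**Step 4: is the difference likely to be deliberate?** Exclusions 9 (systemic infection), 12 (myxoma and cardiac thrombus) and 26 (heparin or an alternative) follow their Section 5.3.3 counterparts closely. Exclusion 27 keeps the nouns of its counterpart but changes the qualifier. That looks like drafting drift, although the documents do not say so.

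**Step 5: effect on the design.** The wording enters no rate, margin, alpha, power or sample size calculation.

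**The case against.** The strongest reply is that the protocol has to be read as a whole. Section 5.3.3 is part of it. Section 8.2 says only that patients meeting the criteria may be considered. Section 9.1 requires a physician investigator to confirm eligibility before RF energy is given. Section 16.2 makes the investigator answerable for use in line with the protocol and the device instructions, and Section 18.4 relies on those directions to limit risk. Since only this catheter may be used, an investigator could fairly treat a contraindication to it as a contraindication to the study ablation and apply exclusion 25.

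Much of this stands. It makes it less likely that such a patient would be treated without anyone noticing. It does not make the answer certain: one site may apply exclusion 25, and another may conclude that exclusion 27, being specific, governs.

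A reader might also infer more than the text supports:
- *That any patient, at any site, is affected.* Section 5.3.3 is confined to the U.S., and Section 5.3.4 leaves other countries to their own lists. Section 7.1 sets a minimum of 50% of sites and subjects from the U.S., so the affected part is substantial but is not the whole study.
- *That a patient with a passable filter is plainly eligible.* On the narrow reading of exclusion 27, every filter patient is excluded.
- *That Table 8-2 fails to carry over other Section 5.3.3 entries, such as hemodynamic instability or congenital and rotational anomalies.* The anomalies are examples under a contraindication to an invasive electrophysiology procedure, which exclusion 25 plausibly covers. A table need not repeat every labelled contraindication, and silence is not a conflict. Exclusion 27 differs because it addresses the condition and sets another test.
- *That the effect on the safety test can be sized.* The documents give no count of such patients, so any number would be an assumption and would show no effect of this wording.

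**Conclusion.** The point holds in a limited form. At U.S. sites, two stated rules give different answers for a patient with a known femoral thrombus that does not prevent femoral insertion. For filters the documents are ambiguous, not contradictory. Exclusion 25 and the instructions-for-use requirement narrow the problem without closing it.

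This is a patient-safety and eligibility-consistency correction for what I assume is a rare situation. It has no effect on sample size, alpha or power. The link to the analysis is one of classification: the reading chosen decides whether such a subject is Consent Ineligible or contributes to the safety endpoints, and that should be settled before any event occurs.

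The conclusion assumes that femoral access is the route used in practice, as Section 10.6.2.2 directs. It takes no position on which clinical rule is right.

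**What to change.** Reconcile the Section 5.3.3 entry with exclusion 27 in both Table 8-2 and the synopsis, so that one test governs at U.S. sites. In the same edit, state:
- whether the qualifier in exclusion 27 applies to filter devices as well as to thrombus;
- whether the device contraindications applicable at a site act as exclusion criteria, so that classification under Sections 9.5.1 and 9.5.4 follows without argument.

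The sponsor's clinical team decides which wording stands. The cost is a wording correction and a notice to sites, with a negligible effect on enrollment expected and no change to the statistical analysis.
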